## **6 DISPOSITION OF SUBJECTS AND DISCONTINUATIONS**

The following will be summarized for all subjects by treatment arm, as counts and percentages of all subjects. Disposition data will be also presented for Safety Population and Pre-administrative Hold Population Subjects.

- Subjects randomized
- Subjects with confirmed eligibility
- Subjects treated with second dose
  - For Rescue and with Recurrence
- Overall number of attacks treated
  - Number of attacks treated with 1 dose
  - Number of attacks treated with 2 doses
- Average number of attacks treated in a 30 day period over participation in the study.
- Subjects in each of the analysis populations:
  - Randomized population
  - ITT population
  - ITT 2nd Dose Population
    - Rescue Population
    - Recurrence Population
  - mITT population
  - Safety population
  - 3-Month Safety Population
  - 6-Month Safety Population

- 12-Month Safety Population
- Duration of time in study for Safety, 6-Month Safety and 12- Month Safety Population (Mean, Median, 25th Quartile, 75th Quartile, SD, Minimum and Maximum)
- Subjects who completed the study for 12 month
  - Treated
  - Not treated
- Discontinued subjects before 12 months
  - Treated
  - Not treated
- Reasons for subject discontinuation
  - Adverse event
  - Death
  - Lost to follow-up
  - Non-compliance with protocol requirements
  - Pregnancy
  - Subject request
  - Investigator request
  - Sponsor request
  - Missing
- Discontinuations within 48 hours of last dose, by reason for discontinuation.

The number and percentage of subjects in each disposition category will be presented; percentages will be based on the number of all subjects. Percentages for the number of subjects randomized will be based on the total number of subjects who enrolled in the study. Percentages for the treated status of discontinued subjects will be based on the number of subjects who discontinued. For discontinuation reasons, percentages will be based on the number of subjects who discontinued. Subjects' inclusion in the analysis populations will be listed. Disposition data and all subjects who discontinue from the study will be presented in a separate listing.

## **7 PROTOCOL DEVIATIONS**

The number and percentage of subjects with protocol deviations will be presented by categories for the randomized population. Additionally, all deviations will be presented in a listing.

## **8 DEMOGRAPHICS AND BASELINE CHARACTERISTICS**

### **8.1 Demographics**

The following will be summarized by treatment group and overall for the Randomized, ITT, 6-Month Population, 12- Month Population, Pre-administrative Hold Population and Safety populations.

- Age

- Gender
  - Female
  - Male
- Race
  - American Indian or Alaska Native
  - Asian
  - Black or African American
  - Native Hawaiian or other Pacific Islander
  - White
  - Other
  - Multiple
- Ethnicity
  - Hispanic or Latino
  - Not Hispanic or Latino
  - Not Reported
  - Unknown
- Height (in)
- Weight (lb)
- Body Mass index (BMI) (kg/m^2)
- Smoking history
  - Never
  - Former
  - Currently
- Family history of coronary artery disease (CAD)
  - Yes
  - No
- Subjects  $\geq 1$  cardiovascular risk factors
- Subjects  $\geq 2$  cardiovascular risk factors
- Parent study
  - COL MIG-301/H8H-CD-LAHJ
  - COL MIG-302/H8H-CD-LAHK
  - Addendum 2 Subjects (This information will not be presented for the Interim Analysis Submission Tables)
- Duration of migraine history (This data will be used from parent study for rollover patients)
- Average migraines/Month in past three months (This data will be used from parent study for rollover patients)
- IHS Diagnostic Criteria: Migraine with Aura- Subjects with Aura consisting of at least one of the following (This data will be used from parent study for rollover patients):

- Use of medications reducing migraines (This data will be used from current 305 study IVRS report)

Age will be calculated using the difference in days between the date of birth and the date of informed consent from parent study.

BMI will be calculated as:

$$\text{Weight (lb)} / \text{height (in)}^2 * 703$$

All demographic data will be presented in a listing.

## **8.2 MIDAS**

Migraine Disability Assessment (MIDAS) total scores, number of days with headaches over the past 3 months, and average headache pain past three months will be summarized by treatment group for ITT population at **Visit 1/Screening, Month 1/ Visit 2, Month 3/Visit 3, Month 6/Visit 4, Month 9/Visit 5 and Month 12/Visit 6 (EoS/ET)**. MIDAS total score will also be presented as change from baseline for each post-baseline visit. The MIDAS is a five-item questionnaire; the MIDAS total score is calculated as the sum of the answers to all five questions. The specifics of the questionnaire are detailed in Appendix 2 of the Protocol.

Average pain is measured on a scale from 0 to 10, where 0 is no pain at all and 10 is pain as bad as it can be. Average days with headache past 3 months will be reported. If headache lasted for more than 1 day, each day will be counted.

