
Study Design: This is a prospective, randomized, open-label study in subjects with migraine who have completed the Phase 3 studies, COL MIG-301 or COL MIG-302. Subjects will be stratified (yes or no) for use of concomitant medications that reduce the frequency of migraine episodes.
 
Subjects will be asked to treat all migraine attacks with study drug on an outpatient basis for up to 12 months. Each patient's study participation will consist of a screening visit (Visit 1) and a treatment period of up to 12 months during which the subject will treat all migraine attacks with either lasmiditan 200 mg or lasmiditan 100 mg (with a second dose of study drug permitted between 2 and 24 hours (h) for recurrence of migraine only for subjects randomized to lasmiditan 100 mg). During the treatment period subjects will return to the clinic at 1, 3, 6, 9 and 12 months. There will be an early termination (ET) visit within two weeks (14 days) of treatment discontinuation for all subjects that discontinue between scheduled visits. The End-of-Study (EoS) visit will be at 12 months or at any scheduled visit when the subject's participation in the study is ended. Participation in the study for 12 months will be defined as completing Month 12/Visit 6.
 
At Screening/Visit 1 subjects will provide written informed consent and authorize Health Insurance Portability and Accountability Act (HIPAA). Study eligibility will be assessed on the basis of completing study COL MIG-301 or COL MIG-302. The EoS/Visit 2 of COL MIG-301 or COL MIG-302 can be the same day as Screening/Visit 1. Assessments required for this visit can be the same assessments obtained at the EoS/Visit 2 of COL MIG-301 or COL MIG-302 as long as that visit occurred on the same day or no more than two weeks prior to signing informed consent and HIPAA for participation in COL MIG-305 as outlined in the Schedule of Assessments (Table 1). Regardless of the timing of
		

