- Time to headache relief and time to pain free after a second dose of lasmiditan for rescue or recurrence of migraine
- MBS free after a second dose of lasmiditan for rescue or recurrence of migraine
- Total number of migraine attacks and attacks treated with study medication over each 3 month

period

Resource utilization:

- Any CV events and/or related resource utilization such as visits to cardiologists, procedures, hospitalizations, new treatments or treatment adjustments for CV disease as collected in study COL MIG-301 or COL MIG-302 compared to on study **Visit 1** through **Visit 6/EoS/ET**.
- Any visits to an emergency room or physician's office for treatment of migraine as collected in study COL MIG-301 or COL MIG-302 compared to on study **Visit 1** through **Visit 6/EoS/ET** excluding study specific visits.
- Concomitant medications for the treatment of migraine and/or pain as collected in study COL MIG-301 or COL MIG-302 compared to concomitant medications for migraine and/or pain **Visit 1** through **Visit 6/EoS/ET**.
- Missed days of work and/or school or daily activities based on responses to MIDAS questionnaire.

Statistical Analysis:

Safety:

Adverse events will be summarized in terms of the proportion of patients and the proportion of attacks associated with any adverse event and with specific adverse events. Physical examinations, vital signs, clinical laboratory parameters (hematology, serum chemistry and urinalysis) and ECG parameters will be summarized in terms of change from baseline status at 1, 3, 6, 9 and 12 months or early termination.

Efficacy:

This is an open-label study with no control group. Efficacy data will be summarized using descriptive statistics. The proportion of attacks treated with study medication which respond at 2 hours will be calculated for each 3 month period.

Resource Utilization:

Resource utilization such as visits to cardiologists, procedures, hospitalizations, new treatments or treatment adjustments for CV disease as well as visits to the emergency room or a physician's office for the treatment of migraine will be summarized by treatment arm in terms of patient reported information recorded in study COL MIG-301 or COL MIG-302 compared to information reported at **Visits 2, 3, 4, 5, and EoS/ET/6**. Concomitant medication use for migraine and/or pain and missed days of work and/or school or daily activities based on responses to MIDAS questionnaire will be summarized by treatment arm.

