5.5.5 EoS/ET/Visit 6 (Month 12)

The following assessments will be performed. This EoS visit is for all subjects completing study through month 12 OR any subject concluding their participation in the study at any scheduled visit. The visit should occur at approximately the same time of day (\pm 1 hour) and 90 days (\pm 4 d) from the last visit and be at least 7 days after the last migraine is dosed. Patient completion through month 12 will be defined as completing **Month 12/Visit 6**. The ET visit is for all subjects discontinuing from the study at any time between scheduled study visits for any reason. The visit should occur within 14 days of the decision to discontinue.

- Collect empty dosing card(s) and all unused study drug and review dosing compliance.
- Review patient diary compliance.
- Collect resource utilization (See Section 9.1.1.3).
- Have patient complete MIDAS questionnaire (See Section 9.1.1.2 and Appendix 2).
- Obtain C-SSRS (See Section 9.1.6 and Appendix 3).
- Assess for AEs and use of concomitant medications.
- Perform a brief symptom-related physical examination if indicated by an AE (See Section 9.1.2.).

- Obtain vital sign readings (See Section 9.1.3).
- Perform a 12-lead ECG (See Section 9.1.4).
- Collect blood and urine samples for clinical laboratory tests (hematology, chemistry, and urinalysis) (See Section 9.1.5). The laboratory tests will include a urine pregnancy test for WOCBP. A positive urine pregnancy test will be confirmed with a serum β HCG test. (The confirmatory test may be run in the local clinical laboratory).
- Subject's participation in study is complete.

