6.4 Subject Withdrawal Criteria

Subjects may voluntarily withdraw from the study, or be removed from the study at the discretion of the Investigator or Sponsor, at any time. The Investigator may withdraw a subject at any time if it is determined that continuing in the study would result in a significant safety risk to the subject.

If such withdrawal occurs, or if the subject fails to return for **Visit 6/EoS/ET** the Investigator should determine the primary reason for a subject's premature withdrawal from the study and record the reason in the subject's study records.

Premature withdrawal may occur for any of the following reasons:

- Non-compliance with the protocol requirements
- Pregnancy
- Death
- Adverse event (AE)
- Subject request
- Investigator request
- Sponsor request

For subjects who are lost to follow-up (i.e., those subjects whose status is unclear because they fail to appear for study visits without stating an intention to withdraw), the Investigator should show "due diligence" by documenting in the source documents all steps taken to contact the subject, e.g., dates of telephone calls, registered letters, etc.

All subjects discontinuing from the trial before a scheduled visit regardless of cause, must be seen for **ET/Visit 6** for safety assessments and to return all unused study drug and the e-diary. Subjects that withdraw from the study prior to dosing a migraine attack should return to the clinic for **ET/Visit 6** to return all unused study drug and the e-diary. Subjects that desire to withdraw from the study at one of the scheduled visits (**Visit 2, 3, 4 or 5**) should complete the **EoS/Visit 6** study assessments and return all unused study drug and the e-diary.

Subjects who are withdrawn from the study for any reason will not be replaced.

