### **8.5 Characteristics of All Treated Migraine Attacks**

The following will be summarized by treatment group for the mITT and ITT population for all treated migraine attacks in each treatment group. Similar information will also be presented by quarter. Quarter will be defined as time interval of 3 months between each nominal visit number recorded in the database starting from screening visit. E. g. **Screening/Visit 1** to **Month 3/Visit 3** with 3 months duration is Quarter 1.

- Time to dosing from the start of migraine attack (hours)
- Baseline migraine severity
  - Severe (3)
  - Moderate (2)
  - Mild (1)
  - None (0)
- Baseline associated symptoms (yes or no)
  - Nausea
  - Phonophobia
  - Photophobia
  - Vomiting
  - None
- Baseline most bothersome symptom
  - Nausea
  - Phonophobia
  - Photophobia
- Second dose of study drug taken before the 2-hour assessment (yes or no)
- Other medications taken to treat migraine (yes or no)
  - No
  - Yes, before 2-hour assessment
  - Yes, after 2-hour assessment

- Number of treated migraine attacks with second dose
  - Treated as Rescue
  - Treated as Recurrence
  - Missing (if any)
- Total number of treated migraine attacks during entire study
- Average number of migraine attacks treated per 30-day period.

Time to dosing from start of the each treated migraine attack (hours) will be calculated as:  
date/time of dosing –  
date/time of start of the acute migraine attack

Date and time of dosing will be taken from the subject e-diary.

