### **11.1 Efficacy analysis of secondary endpoint**

For the secondary endpoint the proportion of attacks treated with lasmiditan 100 mg and with lasmiditan 200 mg which respond as headache pain-free at 2 hours will be calculated for each 3 month period based on the treated migraine-level of the mITT population.

The proportion will be calculated as number of attacks which meet the criteria for headache pain-free at 2 hours divided by total number of treated attacks in each treatment group.

This analysis will be presented by treated migraine attack for total no. of attacks in each treatment group. This data will be presented for each three month period of time such as 0 – 3 months after randomization, > 3 – 6 months after randomization, > 6 – 9 months after randomization, > 9 – 12 months after randomization as well as for the entire study.

Headache pain-free is defined as a reduction in headache severity from mild (1), moderate (2), or severe (3) at baseline to none (0).

Treated migraines that do not have a headache pain severity rating at baseline will be excluded from the analysis. Treated migraines that do not have an associated headache pain severity rating at the two-hour time point will be assumed to have not achieved headache pain-free.

Subjects taking any rescue medication within the first two hours will be assumed to have not achieved headache pain-free. Subjects who use other medication prior to the study drug to treat the migraine attack will also be assumed to have not achieved headache pain-free.

Subjects who treat a no (0) severity migraine will not be included in this analysis.

Similar analysis will also be performed for Most Bothersome Symptoms Free at 2 hours post dose and Headache Pain Relief at 2 hours post dose under the same assumptions of sections 11.2.1.2 and 11.2.1.6 .

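### The Month 12 row for MIDAS and cardiovascular resource use pools 12-month completers with early leavers, and the SAP defines quarters in two different ways

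*SAP*

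**What the plan says.** **One label, three events.** The protocol synopsis states: "The End-of-Study (EoS) visit will be at 12 months or at any scheduled visit when" the subject's participation ends. Protocol 5.5.5 gives the EoS visit to "all subjects completing study through month 12 OR any subject concluding their participation in the study at any scheduled visit". It adds: "The ET visit is for all subjects discontinuing from the study at any time between scheduled study visits for any reason". Protocol 6.4 confirms the numbering: "All subjects discontinuing from the trial before a scheduled visit regardless of cause, must be seen for" ET/Visit 6, and those who leave at Visits 2 to 5 complete the EoS/Visit 6 assessments.

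**How Visit 6 is summarized.** SAP 8.2 lists the MIDAS summary visits up to "Month 9/Visit 5 and Month 12/Visit 6 (EoS/ET" and adds change from baseline at each post-baseline visit. SAP 13 presents cardiovascular resource use at the same combined visit. SAP 12.2, 12.3 and 12.4 use that label for when laboratory, vital-sign and ECG data are collected. The protocol synopsis has the safety measures summarized as "change from baseline status at 1, 3, 6, 9 and 12 months or early termination".

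**Quarters.** SAP 8.5: "Quarter will be defined as time interval of 3 months between each nominal visit number recorded in the database starting from screening visit". The by-quarter summaries of pain-free, MBS-free and pain relief in SAP 11.2 refer back to 8.5. For the secondary endpoint, SAP 11.1 says: "This data will be presented for each three month period of time such as 0 – 3 months after randomization", followed by the later three-month periods.

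**The concern.** A row headed Month 12 should describe subjects at about 12 months. Under this labelling, a subject who stops in week 5 and attends the ET visit is counted beside someone who has treated attacks for a year. The result is neither a 12-month value nor a clean last observation.

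Early leavers may differ from completers in the quantity being measured. Under SAP 2.1, subjects may be discontinued after more than a month without a treated migraine. Under protocol 7.4, those who need new or changed prophylaxis are to be withdrawn. One route selects for low migraine burden and the other probably for high burden, so the direction of any bias is unknown.

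MIDAS adds a further difficulty because it looks back three months (protocol 9.1.1.2): an ET visit in the first three months partly describes time before the study. Weight is scheduled only at Visits 1 and 6 (protocol 9.1.2), so the pooled visit is its only scheduled post-baseline value.

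For quarters, two tables of 2-hour pain-free by period can disagree only because the periods are cut differently, and SAP 8.5 leaves some attacks of early leavers without a stated quarter.

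**Working it through.** **1. When a true Month 12 visit falls.** The intervals in protocol 5.4.1 are 30, 60, 90, 90 and 90 days, with windows of ±2, ±4, ±4, ±4 and ±4.

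- Nominal day: 30 + 60 + 90 + 90 + 90 = 360.
- Accumulated window: 2 + 4 + 4 + 4 + 4 = 18.
- Range: 360 − 18 = 342 to 360 + 18 = 378.

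The upper end reproduces the protocol's stated maximum of 54 weeks: 54 × 7 = 378 days. An ET/Visit 6 has no such window and can fall on almost any study day.

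**2. Share of the Visit 6 row that comes from early leavers.** Let d be the proportion leaving before Month 12 and a the proportion of those who attend an EoS/ET visit. Assume every completer contributes a record. Then

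share = d·a / (d·a + 1 − d).

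The documents give neither d nor a, so both are assumed:

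| d | a | calculation | share |
|---|---|---|---|
| 0.10 | 0.50 | 0.05 / 0.95 | 5% |
| 0.30 | 0.60 | 0.18 / 0.88 | 20% |
| 0.40 | 0.75 | 0.30 / 0.90 | 33% |
| 0.60 | 0.90 | 0.54 / 0.94 | 57% |

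With the planned 2580 subjects, the third line means 2580 × 0.40 × 0.75 = 774 leaver records beside 2580 × 0.60 = 1548 completer records.

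**3. Effect on a mean.** The row mean moves away from the completer mean by share × (leaver mean − completer mean). For an assumed gap of 10 MIDAS points and a share of 33%, that is 3.3 points. With no gap, nothing moves.

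**4. MIDAS recall.** Taking three months as 90 days, a questionnaire at an ET visit on day 35 covers 90 − 35 = 55 days before enrolment.

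**5. Quarters side by side.** Take a subject with Visit 3 on day 90 and ET/Visit 6 on day 130, and the attacks treated between those days.

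- SAP 11.1: more than 3 to 6 months, without ambiguity.
- SAP 8.5, assigned by the opening visit (3): Quarter 2.
- SAP 8.5, assigned by the closing visit number (6): Quarter 4.
- SAP 8.5, if Quarter 4 means only Visit 5 to Visit 6: no quarter.

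The text of 8.5 does not choose among these. Both 11.1 and 11.2 apply their summaries to treated migraines in the mITT population, and both exclude attacks with missing or no pain at baseline.

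**6. Search for a rule that would resolve this.** The visit-window wording in SAP 5 and SAP 10 concerns dosing dates. No SAP section assigns an early Visit 6 assessment to its study month.

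**The case against.** The pooling is open: the row carries the EoS/ET label, and the protocol prespecifies 12 months or early termination as one time point. SAP 6 reports discontinuations before 12 months and time in study, so a reader can see how many left. Nothing is tested on this row. All of that stands, and it rules out calling the row concealed. It does not let a reader separate completers from leavers within the row. The SAP draws the distinction elsewhere: SAP 2.1 excludes early-termination subjects from 12-month participation, and SAP 4 requires 348 days for the 12-month safety population.

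A reader might go further in three ways that the documents do not support.

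- **That later-quarter results contain early dropouts.** This is possible only in summaries that cite SAP 8.5, and only under one programming choice that the SAP does not state. SAP 11.1 uses time since randomization, exposure in SAP 10 is given in month intervals, and the safety populations use 87, 174 and 348 days.
- **That all laboratory and ECG results are affected.** SAP 12.2 and 12.4 use the combined label for collection. By-visit means would inherit it if programmed under that label, but the laboratory shifts use the lowest and highest post-baseline values and the ECG shifts use the worst.
- **That the two quarterly pain-free results differ materially.** For subjects on schedule, visits fall near days 90, 180, 270 and 360. The definitions then differ mainly for attacks near visit boundaries and for early leavers.

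**Conclusion.** The point holds within limits. Followed as written, the plan gives a Month 12 row for MIDAS and cardiovascular resource use that mixes completers with early leavers, and it gives quarterly 2-hour pain-free under two period definitions, one of which is incomplete for early leavers.

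The size cannot be derived from the documents. The 20–57% range depends wholly on the assumed 30–60% dropout and 60–90% attendance, and it is a share of records, not a bias. The bias also needs a difference between leavers and completers, for which the documents give no figure.

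The primary endpoint, the proportion of patients and of attacks with adverse events, does not use the Visit 6 row. The matter is therefore one of interpreting descriptive long-term results. It should be corrected, but it does not threaten the study's main conclusion.

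**What to change.** 1. Add an analysis-visit rule to the SAP: assign EoS and ET assessments to windows by study day, or show early EoS and ET values in a separate early-termination row. Apply it to MIDAS, resource use and the by-visit laboratory, vital-sign and ECG summaries.
2. Limit Month 12 to subjects whose Visit 6 falls in its window, and state the bounds. The visit calendar gives day 342 as the earliest in-window day, while the 12-month safety population starts at day 348. The SAP should say whether that 6-day difference is intended. It should also say how subjects who withdraw at a scheduled visit count towards 12-month participation, since SAP 2.1 excludes only early terminations by name.
3. Replace the SAP 8.5 quarter definition with days since randomization, as in 11.1, for every quarterly summary. Include the by-quarter adverse-event table in SAP 12.1, which names no definition.

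No new data are needed. The cost is a short SAP change, one extra row and a smaller Month 12 n.
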